13.7.7. Discontinuation of Immunosuppressive Medication

Cumulative incidence of discontinuation of all immunosuppression by Days 28, 56, 86 and 180 post-first study treatment with ALXN1007 will be analyzed using similar methods as described above for acute GVHD flares with death as a competing risk.

13.7.8. Non-Relapse Mortality

Cumulative incidence of non-relapse mortality at Days 180 and 360 post-first study treatment with ALXN1007 will be analyzed using similar methods as described above for acute GVHD flares with relapse as a competing risk.

13.8. Safety Analyses

Safety assessments will consist of summarizing all AEs, SAEs, infections and laboratory values including: chemistry panel, coagulation panel, CBC with differential, thyroid function testing and urinalysis results. Changes from Baseline in vital signs and laboratory assessments will be summarized. Shifts from Baseline in laboratory assessments, as well as physical examination findings, will be summarized for the different time points. All safety analyses will be performed on the Safety Set and the modified Safety Set.

13.8.1. Adverse Events

All AEs will be coded using the Medical Dictionary for Regulatory Activities (MedDRA) (version 15.1 or higher).

AEs occurring from the signing of informed consent and prior to the initiation of ALXN1007 treatment (pre-treatment AEs) will be summarized.

Treatment-emergent AEs are AEs with onset after the start of ALXN1007 treatment. TEAEs will be summarized by incidence, Preferred Term, System Organ Class (SOC), seriousness, severity and relationship to treatment.

All AEs, including infections, will be summarized by both event counts and subject counts. For subject counts, if a subject has more than 1 occurrence of an AE for a specific preferred term or SOC, the subject will be counted only once for that preferred term or SOC. The most severe occurrence of an AE as well as the most extreme relationship of the AE will be indicated in cases of multiple occurrences of the same AE.

13.8.2. Laboratory Parameters

Laboratory assessments (chemistry panel, coagulation panel, CBC with differential, thyroid function testing [TPO, TSH, FT-4] and urinalysis) will be summarized by visit. Frequency distribution of abnormal clinical laboratory values will be provided by visit.

13.8.3. Vital Signs, Electrocardiograms, Antibodies to ALXN1007

Vital signs (systolic and diastolic BP, temperature, heart rate, and respiratory rate) and changes from Baseline in vital signs will be summarized by visit. The number and percentage of subjects with ECG findings will be summarized by visit. If a sufficient number of subjects show positive antibody results, the proportion of subjects with antibodies to ALXN1007 post-treatment will be summarized.

13.9. Pharmacokinetic Analyses

PK samples will be assayed for ALXN1007 concentration at Baseline and at the study visits (and time points) outlined in Table 5.

Graphs of plasma ALXN1007 concentration time profiles for individual subjects and for means will be provided. Non-compartmental PK methods will be used to estimate PK parameters of interest (eg, C_{max} , t_{max} , AUC, etc). Actual dosing and sampling times will be used for all calculations. Descriptive statistics will be calculated for PK parameters and plasma concentration data at each sampling time, as appropriate.

Additional model-based exploratory analyses may be performed:

- To explore ALXN1007 PK in healthy (SAD [C11-002] and MAD [ALXN1007-US-HV-102]) and GI GVHD subjects.
- To develop a preliminary population PK model of ALXN1007 in healthy and GI GVHD subjects.
- To explore subject demographics and characteristics predictive of the PK variability of ALXN1007.

13.10. Pharmacodynamic and Exploratory Biomarker Analyses

Summary tabulations of mean, SD, median, minimum and maximum biomarker values will be presented. The relationship between changes in PD biomarkers, exploratory biomarkers and the effects of ALXN1007 treatment outcome will be evaluated.

13.10.1. Exploratory Exposure-Response Analyses

The relationship between plasma ALXN1007 concentration and the key PD and exploratory biomarkers will be assessed by graphical display. Additional model-based exploratory analyses may be performed:

- To explore the PD effects of ALXN1007 on C5a, C5 and terminal complement activity.
- To develop preliminary population PK/PD models of ALXN1007 in humans.
- To conduct an exploratory graphical evaluation to characterize the PK/PD relationships between ALXN1007 exposure and other biomarkers.

Development of these preliminary models may allow simulation based exploration of dose regimens for future studies, as well as determination of the concentration needed to provide target inhibition in the subject population. Development of these models may also provide exposure metrics for correlation of ALXN1007 exposure with safety events (if any). Early development of a PK/PD model can also facilitate optimization of sampling schedule in future studies, potentially reducing sampling load.

14. DIRECT ACCESS TO SOURCE DATA/DOCUMENTS

14.1. Study Monitoring

Before an investigational site can enter a subject into the study, a representative of the Sponsor will visit the investigational study site to:

- Determine the adequacy of the facilities.
- Discuss with the Investigator(s) and other personnel their responsibilities with regard to protocol adherence, and the responsibilities of the Sponsor or its representatives.
 This will be documented in a Clinical Study Agreement between the Sponsor or representative and the Investigator.

During the study, a monitor from the Sponsor or its representatives will have regular contacts with the investigational site, for the following:

- Provide information and support to the Investigator(s).
- Confirm that facilities remain acceptable.
- Confirm that the investigational team is adhering to the protocol, data are being accurately recorded in the eCRFs and that ALXN1007 accountability checks are being performed.
- Perform source data verification. This includes a comparison of the data in the eCRFs with the subjects' medical records at the hospital or practice, and other records relevant to the study. This will require direct access to all original records for each subject (eg, clinic charts).
- Record and report any protocol deviations not previously sent to the Sponsor.
- Confirm AEs and SAEs have been properly documented on eCRFs and confirm any SAEs have been forwarded to the Sponsor or its delegate and those SAEs that met criteria for reporting have been forwarded to the IRB/IEC.

The monitor will be available between visits if the Investigator(s) or other staff needs information or advice.

14.2. Audits and Inspections

Authorized representatives of the Sponsor, a regulatory authority, an IEC or an IRB may visit the site to perform audits or inspections, including source data verification. The purpose of an Alexion audit or inspection is to systematically and independently examine all study-related activities and documents to determine whether these activities were conducted, and data were recorded, analyzed, and accurately reported according to the protocol, Good Clinical Practice (GCP) guidelines of the ICH, and any applicable regulatory requirements. The Investigator should contact the Sponsor immediately if contacted by a regulatory agency about an inspection.

14.3. Institutional Review Board/Independent Ethics Committee

The PI or Sponsor designee, depending on the country requirements, must obtain IRB/IEC approval for the investigation. Initial IRB/IEC approval, and all materials that have been submitted and approved by the IRB/IEC for this study, including the subject informed consent form (ICF) and recruitment materials, must be maintained by the Investigator and made available for inspection.

14.4. Data Monitoring Committee

An independent DMC will be established for the study. The DMC will be responsible for conducting interim monitoring of safety data throughout the treatment period of the study. In addition, for Cohort 2 (the 20 mg/kg QW dosing regimen), Cohort 3 (the 20 mg/kg twice weekly dosing regimen) and any additional dosing cohorts exploring a higher dose than Cohort 1 (ie, 10 mg/kg per week), after the first 3 subjects have completed the Day 28 procedures and assessments (ie, received all protocol prescribed ALXN1007 doses through Day 28), the DMC will convene to review aggregate safety and tolerability (as well as any available PK/PD) data and recommend that the dose be escalated (as applicable), continued within the cohort, or decreased to the previous dose level or to a dose between the planned dose levels. Final dosing decisions will be made by the Sponsor, in consultation with the DMC, based on safety, tolerability and any available PK/PD data.

At the discretion of the Sponsor, and in consultation with the DMC, other dosing cohorts (not to exceed a total dose of 40 mg/kg/per week for 8 weeks) may also be explored based on cumulating safety and tolerability data as well as any PK/PD data that may be available.

The DMC will include at least 1 physician who is an expert in transplant infectious diseases, one physician who is a hematologist/oncologist with expertise in management of GVHD and one statistician, none of whom is affiliated with the Sponsor.

A separate DMC Charter will document all DMC procedures and processes for the study.

15. QUALITY CONTROL AND QUALITY ASSURANCE

To ensure compliance with GCPs and all applicable regulatory requirements, the Sponsor may conduct a quality assurance audit. Please refer to Section 14.2 for more details regarding the audit process.

16. ETHICS

16.1. Ethics Review

The final study protocol, including the final version of the ICF, must be approved or given a favorable opinion in writing by an IRB or IEC as appropriate. The Investigator must submit a copy of the written approval to the Sponsor or its designee before he or she can enroll any subject into the study.

The PI, or Sponsor/designee depending on the country requirements, is responsible for informing the IRB or IEC of any amendment to the protocol in accordance with local requirements. In addition, the IRB or IEC must approve all advertising used to recruit subjects for the study. The protocol must be re-approved by the IRB or IEC upon receipt of amendments and annually, as local regulations require.

The PI is also responsible for providing the IRB/IEC with reports of any reportable serious adverse drug reactions from any other study conducted with ALXN1007. The Sponsor or its designee will provide this information to the PI.

Progress reports and notifications of serious adverse drug reactions will be provided to the IRB or IEC according to local regulations and guidelines.

16.2. Ethical Conduct of the Study

The study will be performed in accordance with ethical principles that have their origin in the Declaration of Helsinki and are consistent with ICH/GCP and applicable regulatory requirements.

16.3. Written Informed Consent

The PI(s) at each study site will ensure that the subject is given full and adequate oral and written information about the nature, purpose, possible risk and benefit of the study. Subjects must also be notified that they are free to discontinue from the study at any time. The subject should be given the opportunity to ask questions and allowed time to consider the information provided.

The subject's signed and dated informed consent must be obtained before conducting any study procedures.

The PI must maintain the original, signed ICF. A copy of the signed ICF must be given to the subject.

17. DATA HANDLING AND RECORDKEEPING

17.1. Inspection of Records

The Sponsor or its designee will be allowed to conduct site visits to the investigation facilities for the purpose of monitoring any aspect of the study. The Investigator agrees to allow the monitor to inspect the drug storage area, ALXN1007 stocks, drug accountability records, subject charts and study source documents, and other records relative to study conduct.

17.2. Retention of Pharmacodynamic, Pharmacogenetic and Exploratory Biomarker Biological Samples

If a subject has provided consent for long-term storage of biological samples, and if permitted by local regulatory authorities, any remaining biological samples will be stored at a central location or Alexion laboratory for a maximum of 15 years after the last subject's last study visit or longer, if permitted by regulatory authorities. The stored samples will not be used for any purpose other than as outlined in this protocol. The biological samples and other clinical study data for analysis in this study will be single coded for de-identification. The link between the subject enrollment number and any bioanalytical or genetic results (if authorized) will be maintained and stored in a secure environment, with restricted access. The link will be used to identify the relevant samples for analysis, facilitate correlation of biochemical or genetic results with clinical data, allow regulatory audit, and to trace samples for destruction in the case of withdrawal of consent when the subject has requested disposal/destruction of collected samples not yet analyzed.

17.3. Retention of Records

The PI must maintain all documentation relating to the study for a period of 2 years after the last marketing application approval or, if not approved, 2 years following the discontinuance of the test article for investigation. If it becomes necessary for the Sponsor, its designee or the regulatory authority to review any documentation relating to the study, the Investigator must permit access to such records. The PI must maintain confidential all study documentation, and take measures to prevent accidental or premature destruction of these documents.

18. PUBLICATION POLICY

The terms for publication are outlined in the Clinical Study Agreement, Statement of Agreement or the Master Clinical Study Agreement. Refer to these documents for further details and information.

APPENDIX 1. MODIFIED KEYSTONE GRADING SCHEMA

Modified Keystone Grading Schema

	Stage 0	Stage 1	Stage 2	Stage 3	Stage 4
Skin	No Rash	Rash <25%	25-50%	>50%	Bullae and
		BSA	BSA	BSA	desquamation
Lower	<500 ml/day	500-	1001-	>1500 ml/ day	Severe
GI Tract	stool volume	1000 ml/day	1500 ml/day	stool volume	abdominal pain
1		stool volume	stool volume		+/- ileus, frank
					blood or melena
Liver ²	≤2 mg/dl	2.1-3 mg/dl	3.1-6 mg/dl	6.1-15 mg/dl	>15 mg/dl

Abbreviations: BSA = body surface area; GI = gastrointestinal (Przepiorka, 1995)

¹ Lower GI tract assessment consists of determination of stool volume over a 24-hour period. Detailed instructions for determining stool volume can be found in the Study Operations Manual (SOM) for the study.

² Values presented for each stage are bilirubin level.

APPENDIX 2. VERY GOOD PARTIAL RESPONSE (VGPR) CRITERIA FOR ACUTE GVHD (MARTIN, 2009)

Skin

• No rash, or residual erythematous rash involving <25% of the body surface, without bullae (residual faint erythema and hyperpigmentation do not count)

Liver

• Total serum bilirubin concentration <2 mg/dL or <25% of the value at diagnosis

Gut

- Tolerating food or enteral feeding
- Predominantly formed stools
- No overt gastrointestinal bleeding or abdominal cramping
- No more than occasional nausea or vomiting

APPENDIX 3. CLINICAL LABORATORY TESTS

Chemistry Panel

Sodium

Potassium

Chloride

Bicarbonate

Blood urea nitrogen (BUN)

Creatinine

Glucose

Alkaline phosphatase

Alanine aminotransferase (ALT)

Aspartate aminotransferase (AST)

Total bilirubin

Albumin

Total protein

Uric acid

Complete Blood Count (CBC) with Differential

White blood cell (WBC) count

WBC differential

Red blood cell (RBC) count

RBC mean corpuscular volume (MCV)

RBC distribution width

Hemoglobin

Hematocrit

Platelet count

Urinalysis

Appearance

Specific gravity

рΗ

Protein

Blood

Glucose

Ketone

Bilirubin

Urobilinogen

Nitrite

Coagulation Panel

Prothrombin time (PT)

Partial thromboplastin time (PTT)

Thyroid Function Tests

Thyroid-stimulating hormone (TSH)

Free Thyroxine (FT-4)

Thyroid Peroxidase Antibody (TPO)

Creatine Phosphokinase (CPK)

Pregnancy test (Human Chorionic Gonadotropin)

Clostridium difficile culture (stool sample)

**Table 1. Abbreviations and acronyms**

Abbreviation or acronym	Explanation
Ab	Antibody
AChR	Acetylcholine receptor
AE	Adverse event
BP	Blood Pressure
C5	Complement protein 5
cm	Centimeters
C MAX	Maximal concentration
C MIN	Minimal concentration
ECG	Electrocardiogram
eCRF	Electronic Case Report Form
FAS	Full Analysis Set
HAHA	Human Anti-human Antibody
HR	Heart Rate
IP	Investigational Product
IST	Immunosuppressant Therapy
IV	Intravenous
IVIg	Intravenous immunoglobulin
LOCF	Last Observation Carried Forward
mAb	Monoclonal Antibody
MedDRA	Medical Dictionary for Regulatory Activities
PD	Pharmacodynamics
PK	Pharmacokinetics
PP	Per Protocol Population
PT	Preferred Term (MedDRA)
PTAEs	Pre-Treatment Adverse Events
RR	Respiration Rate
SAS®	Statistical Analysis Software®
SAE	Serious Adverse Event
SAP	Statistical Analysis Plan
SOC	System Organ Class (MedDRA)
TEAEs	Treatment-Emergent Adverse Events
WHODrug	World Health Organization Drug Dictionary
GVHD	Graft Versus Host Disease
GI-GVHD	Gastro-Intestinal Graft Versus Host Disease
CR	Complete Response
PR	Partial Response
NR	No Response
MR	Mixed Response
VGPR	Very Good Partial Response

## **4. Description of the Protocol**

ALXN1007-GIGVHD-201 is a phase 2a proof of concept study of ALXN1007 in subjects with newly diagnosed acute graft-versus-host disease (GVHD) involving the lower gastrointestinal (GI) tract (GI GVHD). This study will investigate whether targeting complement through C5a inhibition with ALXN1007 may improve outcomes for subjects with newly diagnosed acute GI GVHD. Following up to a 3-day screening period, eligible subjects will receive 10 mg/kg ALXN1007 administered intravenously (IV) once a week for 8 weeks (Cohort 1), OR 20 mg/kg once a week for 8 weeks (Cohort 2), OR 20 mg/kg twice a week for 8 weeks (Cohort 3). Subjects will be followed for efficacy and safety through Day 180 and subject survival status will be collected at Day 360. Approximately 30 subjects confirmed by biopsy to have GI GVHD will be evaluated during this study.

The objectives of this trial are to evaluate the safety, tolerability, pharmacokinetics/pharmacodynamics (PK/PD) and efficacy of IV ALXN1007 in subjects with acute GI GVHD of the lower GI tract.

### **4.1. Changes from Analyses Specified in the Protocol**

Following changes in analyses specified in the protocol are noted:

- Safety analyses will be only performed on safety set as opposed to both safety set and modified safety set as mentioned in the protocol.
- Demographics, baseline characteristics and medical history will be only summarized for safety set as opposed to safety set, modified full analysis set and per-protocol set as mentioned in the protocol.
- The imputation rule has been modified from that described in the protocol for overall acute GVHD response, acute GI-GVHD response and acute GVHD response involving all organs.

In addition due to early termination of the study, an abbreviated CSR will be written and a number of pre-specified analyses will not be performed however by-patient listings will be generated for all data collected for this study.

### **4.2. Changes from Analyses Specified in the Previous Version of the SAP**

See section 4.1.

## 5. DEFINITIONS

### 5.1. Efficacy

#### Secondary Therapy

A key factor in several of the efficacy parameters is determination of secondary therapy (re-escalation of steroid and/or additional intervening therapy) which may consist of any of the following changes to background therapy during the study treatment period:

1. Re-escalation: 2.5mg/kg/day prednisone equivalent for 2 consecutive days starting on or after Day 6 (note, the day of 1st ALXN1007 is denoted by Day 1 for analysis purpose)
2. Additional systemic therapy for treatment of GVHD (including but not limited Biologics/anti-TNF or Antineoplastic medications administered post-baseline for treatment of GVHD)

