6.1.2. Treatment Period (Baseline - Day 56)

The first dosing cohort (Cohort 1) will receive 10 mg/kg ALXN1007 administered IV QW for 8 weeks. With approval of Amendment 6, Cohort 2, 20 mg/kg QW for 8 weeks, will be added to the study. An additional cohort, 20 mg/kg twice weekly for 8 weeks (Cohort 3), is planned after DMC review of safety and tolerability data at Day 28 on the first 3 patients in Cohort 2. At the discretion of the Sponsor, and in consultation with the DMC, other dosing cohorts (not to exceed a total dose of 40 mg/kg per week for 8 weeks) may also be explored as described in Section 6.3.

Review of biopsy histology for confirmation of GI GVHD will occur when biopsy results are available. For subjects without histologically confirmed GI GVHD, refer to Section 6.1.5 for guidance on discontinuing ALXN1007 treatment and conducting an ET visit.

The first ALXN1007 dose will be administered at Baseline. Following this, subjects will receive once weekly dosing until Day 49, or twice weekly dosing until Day 52 (if twice weekly dosing schedule is being administered). On Day 56, subjects will undergo follow-up evaluations but will not receive ALXN1007 treatment.

Each visit during the Treatment Period (including Day 56) should occur at the day indicated \pm 2 days (if the subject is on a weekly dosing schedule) or \pm 1 day (if the subject is on a twice weekly dosing schedule). For subjects on a weekly dosing schedule, there should be a minimum of 4 days between ALXN1007 doses. For subjects on a twice weekly dosing schedule, there should be a minimum of 2 days between ALXN1007 doses. If the recommended acceptable windows cannot be observed, the Sponsor or its representative must be contacted prior to scheduling a visit.

All doses of ALXN1007 will be administered as a continuous IV infusion. Subjects will remain under observation for 2 hours after the infusion. Refer to Sections 9.4 and 9.5, as well as the Pharmacy Manual, for procedures pertaining to the preparation and administration of ALXN1007.

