## 5.1.2. Other Efficacy Endpoints

### 5.1.2.1. Acute GI GVHD response

Acute GI-GVHD responses will be derived based on the following order (Progression, NR, MR, PR and CR) and these responses are mutually exclusive. The effect of secondary therapy only needs to be applied to 'NR' and no need to apply separately to MR, PR and CR because of inherent ordering.

- **Progression:** deterioration in lower GI tract staging (positive change from baseline).
- **No Response (NR):** no change in lower GI tract staging OR receiving secondary therapy.
- **Mixed Response (MR):** improvement in lower GI tract AND deterioration in another organ.
- **Partial Response (PR):** improvement in lower GI tract (provided lower GI tract staging is not 0) AND no deterioration in another organ.
- **Complete Response (CR):** lower GI tract Stage = 0

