### 5.1.2.2. Response for All Organs Involved with Acute GVHD

Acute all organ-GVHD responses will be derived based on the following order (Progression, NR, MR, PR and CR) and these responses are mutually exclusive. Note, the effect of secondary therapy only needs to be applied to 'NR' and no need to apply separately to MR, PR and CR.

- **Progression:** Deterioration in at least 1 organ AND no improvement in other organs
- **No Response (NR):** no change in any organ OR receiving secondary therapy
- **Mixed Response (MR):** Improvement in at least 1 organ AND deterioration in another organ
- **Partial Response (PR):** Improvement in at least 1 organ AND no deterioration in another organ (provided not all stages are 0)
- **Complete Response (CR):** all organ stages are 0

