#### **7.2.1.1. Handling of Dropouts or Missing Data**

- Imputations will be performed up to Day 180 visit (maximum visit for stage data)
- If a patient has been administered with secondary therapy or died before the next missing visit, all subsequent missing values will be imputed as NR (non-responder), otherwise, last non-missing response will be carried forward.

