#### **7.2.1.5. Sensitivity Analyses**

Observed response rates (without any imputation) at Day 28 will be tabulated along with 95% Clopper-Pearson exact confidence intervals. In addition, both imputed and observed results will be presented at all study visits.

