### **Imputation technique for missing acute GI-GVHD and all organ-GVHD response**

- There could be two types of missing data
  - Missing data at intermediate visits (for example, patient may miss Day 28 visit but still has data on Day 21 and 35).
  - Missing data due to discontinuation or deaths.
- Imputations will be performed up to Day 180 visit (maximum visit for stage data)
- For missing visits due to death, all subsequent visits will be imputed as “progression” (irrespective of secondary therapy); note, the protocol defined visit windows can be either  $\pm 2$  or  $\pm 15$  days depending on whether they fall in the treatment-period vs. follow-up period. However, the analysis windows are wider than protocol defined visit windows; if death occurs within a pre-specified analysis window for a particular visit (even if the target day for that visit is less than the day of death), missing values will be considered as ‘progression’.
  - Example: non-missing responses on Day 7, secondary therapy starting on Day 9, death on day 10, Day 14 onward – impute as progression.
- If all post-baseline responses are missing due to an early death, then missing responses will be imputed as “progression”.
- For other missing visits, following imputation rules will be implemented:
  - If the previous observed response is “Progression”, then subsequent missing visits will be imputed as “Progression” irrespective of secondary therapy
  - If response is not “progression” at the previous visit and a patient has been administered with secondary therapy since then, all subsequent missing visits will be imputed as NR
    - Example: Day 14 is CR, Day 28 and Day 35 visits are missing
      - If no secondary therapy flag before Day 28, then Day 28 response will be imputed as CR
      - If secondary therapy administered before Day 28, both Day 28 and 35 missing responses will be imputed as NR
  - Otherwise, carry forward the last non-missing response. Only post-baseline responses are carried forward. If first post-baseline response is missing and the patient did not die, no response can be carried forward.

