**Table 5. Cumulative Stopping Probabilities for Mortality Rates at Day 56**

Evaluation (t)	Total N	X t	Cumulative Probabilities of Stopping at Evaluation (t) with Observed Mortality Rates	
			0.20	0.40
1	6	4	1.7%	17.9%
2	12	6	1.9%	33.5%
3	18	8	1.6%	43.7%
4	24	10	1.3%	51.0%
5	30	11	2.6%	71.0%

- A brief interim safety report summarizing AEs and SAEs will be generated when the first six patients have completed the day 86 visit. This will include all the AE and SAE summary tables and listings mentioned in this SAP. Note: This report will be generated after the 6th patient completes the day 86 visit. This report will include the first 6 patients only with all the safety data available at the time of data cut.
- Additionally, an informal interim analysis will occur after all patients have completed Day 56, which is the end of the treatment period. This interim analysis will

summarize the primary endpoint and other efficacy endpoints, up to day 56 assessment, with the exception of overall survival and non-relapse mortality. In terms of safety, treatment emergent AEs and SAEs will be summarized with all safety data available. The interim analyses will also summarize PK and PD results. Summary tables and listings will be produced for the following parameters as mentioned in this SAP: Enrollment Status, Patient Disposition (Treatment Period), Demographics, Primary Endpoint, Other Efficacy Endpoints (except overall survival and non-relapse mortality), Concomitant medications, treatment emergent AEs and SAEs.

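### GVHD therapy added after Day 56 is not counted as secondary therapy, so a subject rescued late can be scored a complete or partial responder at Days 86 and 180

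*SAP*

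**What the plan says.** SAP 5.1 opens by calling secondary therapy a key factor in several efficacy parameters, "which may consist of any of the following changes to background therapy during the study treatment period". The two components are steroid re-escalation and additional systemic GVHD therapy.

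Both documents date that period. Protocol 6.1.2 is headed "Treatment Period (Baseline - Day 56", and SAP 7.4 refers to "Day 56, which is the end of the treatment period".

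The response categories are derived in the order Progression, NR, MR, PR, CR. SAP 5.1.2.1 says: "The effect of secondary therapy only needs to be applied to 'NR", and that MR, PR and CR need no separate condition. GI complete response then depends on stage alone. For all organs, SAP 5.1.2.2 defines NR as "no change in any organ OR receiving secondary therapy".

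The time span of the tables is longer. SAP 7.2.1.1 states: "Imputations will be performed up to Day 180 visit (maximum visit for stage data"; the rules for GI and all-organ response say the same. SAP 7.2.1.5 adds that "both imputed and observed results will be presented at all study visits", and SAP 7.2.2.1 tabulates the GI and all-organ categories at all visits. Staging is scheduled at Days 86 and 180 (Protocol Tables 3 and 4).

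**The concern.** In this trial a response means improvement without added GVHD therapy. Protocol 10.2.1 and 10.2.2 make that a condition of CR and PR and put no end date on it. If the SAP stops looking for added therapy at Day 56 but goes on scoring response to Day 180, patients whose improvement followed rescue treatment can be reported as responders.

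The abbreviated CSR gives little other protection. Treatment failure and flares, the two endpoints that would bring late rescue to light, are not analysed there (SAP 5.1.2.4 and 5.1.2.5).

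**Working it through.** The plan states no figure to reproduce on this point. The check is to apply the SAP's ordered GI rule under two windows and compare.

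**Inputs.**
- Secondary therapy counts to Day 56 (SAP 5.1 with Protocol 6.1.2 and SAP 7.4), or without an upper limit (Protocol 10.2.1).
- Post-baseline staging visits: Days 7, 14, 21, 28, 35, 42, 49, 56, 86 and 180. That is 10 visits, of which 2 fall after Day 56.
- A hypothetical subject at lower GI stage 3 at diagnosis, with no other organ worse.

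**Rule.** Stage above baseline gives Progression; otherwise unchanged stage or secondary therapy gives NR; otherwise MR if another organ is worse; otherwise PR if the stage is above 0; otherwise CR.

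Each cell shows the result with the Day 56 limit, then without it.

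| Added therapy starts | Day 28 (stage 2) | Day 56 (stage 1) | Day 86 (stage 0) | Day 180 (stage 1) |
|---|---|---|---|---|
| Day 20 | NR / NR | NR / NR | NR / NR | NR / NR |
| Day 50 | PR / PR | NR / NR | NR / NR | NR / NR |
| Day 60 | PR / PR | PR / PR | **CR / NR** | **PR / NR** |
| Day 100 | PR / PR | PR / PR | CR / CR | **PR / NR** |

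**Missing visits.** Take a subject with CR at Day 56, therapy added on Day 60, and Days 86 and 180 missing for a reason other than death. With the limit, the secondary-therapy rule does not apply and the last rule does: "Otherwise, carry forward the last non-missing response". Both visits become CR. Without the limit, both are NR. SAP 7.2.1.1 has the same effect on overall response.

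**Direction.** Progression ranks ahead of NR, so it is unaffected. A subject with no change is NR either way. Only improved subjects move, from NR to MR, PR or CR. Under imputation, NR is replaced by the last response. No subject moves down.

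**Size.** One misclassified subject adds 1/N to a visit's rate:
- n=6: 1/6 = 16.7 points
- n=18: 1/18 = 5.6 points
- n=30: 1/30 = 3.3 points
- n=36: 1/36 = 2.8 points

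The documents give no rate of late second-line therapy. If there are 1 to 3 such subjects (an assumption), the shift is 5.6 to 16.7 points at n=18 (3/18 = 16.7%) and 3.3 to 10.0 points at n=30 (3/30 = 10.0%). As an illustration, 9/18 is 50.0% (Clopper-Pearson 95% CI 26.0 to 74.0) and 10/18 is 55.6% (30.8 to 78.5).

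**Are the data there?** Protocol 8.2 ends general medication recording 30 days after the last dose: nominally Day 49 + 30 = Day 79 on weekly dosing, or Day 52 + 30 = Day 82 on twice-weekly dosing, and earlier for subjects who stop early. After that it asks only for treatments of SAEs, to Day 180. Tables 3 and 4, 10.2.5 and 10.2.6 call for recording at Days 86 and 180, while 6.1.3 asks for it but points back to 8.2. A site could follow either rule.

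**The case against.** The strongest reply is that the limit is loose drafting. The SAP does not formally define its study treatment period. Item 2 of the same definition speaks of medications given post-baseline, SAP 5.1.1 excludes additional therapy without a date, and SAP 7.1.4 lists secondary therapies over the whole study. The limit may well be unintended. That is a reason to correct it: the sentence that governs the flag is the one that would be programmed, and the listing could then contradict the response table.

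The reach is also limited, and this stands. Protocol 5.2.2 names response time points only up to Day 56, and nothing is formally tested. Observed overall response keeps its own undated therapy condition in SAP 5.1.1, so it is exposed mainly through carry-forward; the direct effect is on the GI and all-organ category tables. However, Protocol 13.7.1 and 13.7.2 plan overall and GI response by visit, so the late displays are not merely a SAP addition.

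The by-patient listings would let a careful reader find a late-rescued subject scored as a responder. That does not correct the tabulated rate.

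On Protocol 8.2, the schedule and Section 10.2 already cover much of the need, and an edit to the protocol has little prospective value after early termination. That part is secondary.

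**Conclusion.** The concern holds. As written, SAP 5.1 lets therapy added after Day 56 go uncounted in response tables that run to Day 180, contrary to the protocol's response definitions and without a declaration in SAP 4.1. The misclassification is upward only and can affect 2 of 10 post-baseline staging visits. Results at Days 14, 28 and 56, including the primary endpoint, do not change.

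This rests on reading the treatment period as Baseline to Day 56, as both documents describe it. The total bias is unknown, because neither the number of late-treated subjects nor the final cohort sizes are given; the denominators used above are planned figures. It should be corrected before the tables are produced, but it does not threaten the primary result.

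**What to change.** In SAP 5.1, replace the treatment-period limit with wording such as *at any time from first dose up to the visit being scored*, leaving items 1 and 2 as they are. This agrees with SAP 5.1.1 and 7.1.4 and carries through to the NR and imputation rules without further edits.

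Stopping the response tables at Day 56 would also remove the mismatch. It would drop by-visit results that Protocol 13.7.1 and 13.7.2 plan, so it would have to be declared in SAP 4.1.

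Reconcile Protocol 8.2 with Tables 3 and 4 and Sections 6.1.3, 10.2.5 and 10.2.6, so that corticosteroids, immunosuppressants and topical or systemic GVHD therapy are recorded through Day 180 whatever the date of the last dose. For subjects already followed, confirm that the late therapy data are complete and retrieve gaps from source records.

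The cost is one phrase in the SAP, one bullet in the protocol, and some extra medication entry or retrieval for the existing Day 86 and Day 180 visits.
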